9.3.1 Collection of Specimens

Ten mL of blood will be collected into one lavender top (K2EDTA) tube at each of the following time points:

- Cycle 1 Day 1 (prior to start of study treatment)
- Cycle 5 Day 1 (at the time of first restaging evaluation, prior to treatment)
- Cycle 9 Day 1 (at the time of second restaging evaluation, prior to treatment)
- End of treatment

9.3.2 Handling of Specimens

For plasma samples:

- 1. Invert tubes 10 times to mix blood
- 2. Centrifuge at 4°C at 2500 x g for 15 minutes (or in accordance with centrifuge manufacturer's instructions)
- 3. Remove plasma from each tube and transfer equally into two separate clean 15ml polypropylene tubes
- 4. Repeat centrifuge at 4°C at 2500 x g for 15 minutes (or in accordance with centrifuge manufacturer's instructions)
- 5. Aliquot approximately 1.0ml of plasma from each tube into each 2.0ml cryovial. For the EDTA, aliquot into pink capped cryovial. Total of 4 pink capped cryovials needed for EDTA plasma.
- 6. Label and freeze at -80°C* (see labeling instructions below)
- If the participating site does not have a -80°C freezer, samples should be shipped on dry ice on the day of collection. If unable to ship samples on the day of collection, please place the samples on dry ice until they can be shipped. Samples can be stored on dry ice for no more than 48 hours prior to shipping. Please replenish dry ice as needed to ensure samples stay frozen and there is enough to last throughout shipment.
- Biomarker assays are time sensitive. Samples must be processed within one hour of collection. Complete the Biomarker Flowsheet, insert a copy of the flowsheet with shipment, and fax to ATTN: BIOMARKER LABORATORY at [contact].
- Any questions regarding biomarker processing, supplies and shipping, should be directed to [contact]

All samples have appropriate chain-of-custody documentation to ensure compliance with FDA and IRB regulations. Systems are in place detailing the location, transfer, and use of any and all human research subject samples. Any discrepancies or omissions in flow sheets and/or sample labels are resolved upon

receipt of the sample in the lab. All sample and data handling procedures will be fully compliant with the Health Insurance Portability and Accountability Act of 1996 (HIPAA).

9.3.3 Shipping of Specimens

Plasma samples will be stored for future translational studies with blood based angiome-profiling.

Plasma-containing tubes need to be labeled with the following information (using a Sharpie or Cryopen):

- Protocol Name
- Subject Study Number
- Subject Initials
- Sample Date and Time
- Sample Type (ie. whole blood, EDTA plasma, citrate plasma, serum, urine)

Biomarker samples will be shipped within 48 to 72 hours of completed processing with a completed Biomarker Flowsheet with shipment.

All biomarker samples (whole blood, plasma, serum and urine) must be shipped on dry ice by overnight delivery Monday through Thursday (no holidays) to the following address:

Phase I Biomarker Laboratory ATTN: [name] Duke University Medical Center [name]

9.4 Blood for Cell-Free DNA

The analysis of cell free or circulating tumor DNA is a promising area of investigation that allows for interrogation of tumor-specific molecular alterations in the circulation. One of the key advantages of cfDNA analyses is the high degree of specificity offered, because mutations found in cfDNA are in essence integral agents of an individual's cancer and are defined by their presence in tumor DNA and absence in matched normal DNA. In terms of sensitivity, levels of cfDNA are abundant in most patients with advanced cancer, allowing for the assessment of molecular heterogeneity, monitoring of tumor dynamics, identification of genetic determinants for therapy, tracking of genomic evolution, and development of acquired resistance.⁴⁰

9.4.1 Collection of Specimens

Ten mL of blood will be collected into EDTA tubes prior to treatment at each of the following time points:

- Cycle 1 Day 1
- Cycle 3 Day 1
- Cycle 5 Day 1
- Cycle 7 Day 1
- Cycle 9 Day 1
- End of treatment

9.4.2 Handling of Specimens

See Section 9.3.2

9.4.3 Shipping of Specimens

Plasma samples will be stored for future translational studies using circulating cell-free DNA.

See Section 9.3.3

9.5 HER-2 Status Collection

Because of its involvement in the development of different types of cancer, HER-2 gene/protein status information will be collected for all patients during the study. No formal testing will take place but information will be obtained from prior testing available in medical records or tests that have occurred for other medical reasons during the trial as a part of routine medical care.

10.0 STUDY CALENDAR

Screening/baseline evaluations are to be conducted within 28 days prior to start of protocol therapy. Cycles are 14 days long but may be extended to up to 21 days at physician discretion.

	Screening	Day 1 of each cycle (±/- 3 days)	Every 8 weeks (+/- 3 days	EOT (+/- 3 days)	F/U ¹
Informed consent	X				
Demographics and medical history	X				
ECOG PS, Vitals, weight	X	X			
Height	X			X	
Physical exam	X	X		X	X^5
EKG	X X				
CBC	X	X		X	
CMP	X	X		X	
PTT/INR	X				
Urinalysis or Urine Dipstick ⁶	X	X		X	
β-hCG ²	X				
Imaging ³ and RECIST 1.1 time point response	X		X	X^4	
Ramucirumab		X			
Irinotecan		X			
Tumor Biopsy (Wash U only)	X^7				
Blood for angiome profiling			nt on C1D1, C5D1, . C9D1	X	
Blood for cfDNA			nt on C1D1, C3D1, D1, and C9D1	X	
Collection of HER2 status	At some point during the study				
Adverse event assessment	X			X	X
Survival information					X

- 1. 30 days after EOT visit, then every 2 months. AEs only collected for 30 days after treatment discontinuation.
- 2. Women of childbearing potential only
- 3. Imaging (CT or MRI) will be performed every 8 weeks, +/- 7days, regardless of dosing/cycle delays up to 1 year. After 1 year, the imaging frequency is at the discretion of the treating physician. Information from lesion evaluation by imaging done as part of routine care will be collected until progressive disease has been objectively determined if the patient discontinued treatment due to any other reason than progressive disease.
- 4. EOT imaging not required if most recent scan has been performed within 21 days prior to EOT.
- 5. Physical exam will only be done if the follow-up visit involves an in-person office visit.
- 6. A urine dipstick may be performed in lieu of a full urinalysis, however, if the dipstick is abnormal, confirm urine protein with a full urinalysis. If urinalysis or dipstick shows protein ≥ 2+, a 24-hour urine collection must be collected.
- 7. If safe and feasible, biopsies are to be performed at least 7 days prior to the planned C1D1. See Section 9.1 for additional information.

11.0 DATA SUBMISSION SCHEDULE

Case report forms with appropriate source documentation will be completed according to the schedule listed in this section.

Case Report Form	Submission Schedule	
Original Consent Form	Prior to registration	
Registration Form		
Eligibility Form	Prior to starting treatment	
On-Study Form		
Treatment Form	Every cycle	
Toxicity Form	Continuous	
Correlative Form	Per protocol	
Treatment Summary Form	Completion of treatment	
Follow Up Form	Every 2 months	
Tumor Measurement Form	Submit at imaging time points. See section 10.0 for	
	imaging time points.	
MedWatch Form	See Section 7.0 for reporting requirements	

Any queries generated by Washington University must be responded to within 28 days of receipt by the participating site. The Washington University research team will conduct a regular review of data status at all secondary sites, with appropriate corrective action to be requested as needed.

11.1 Adverse Event Collection in the Case Report Forms

All adverse events that occur beginning with start of treatment (minus exceptions defined in Section 7.0) must be captured in the Toxicity Form. Baseline AEs should be captured on the Toxicity Form.

Participant death due to disease progression should be reported on the Toxicity Form as grade 5 disease progression. If death is due to an AE (e.g. cardiac disorders: cardiac arrest), report as a grade 5 event under that AE. Participant death must also be recorded on the Death Form.

12.0 MEASUREMENT OF EFFECT

12.1 Antitumor Effect – Solid Tumors

For the purposes of this study, patients should be re-evaluated for response every 8 weeks regardless of dosing/cycle delays. In addition to a baseline scan, confirmatory scans should also be obtained not less than 4 weeks following initial documentation of objective response.

Page 40 of 64

Information from lesion evaluation by imaging done as part of routine care will be collected until progressive disease has been objectively determined if the patient discontinued treatment due to any other reason than progressive disease.

Response and progression will be evaluated in this study using the new international criteria proposed by the revised Response Evaluation Criteria in Solid Tumors (RECIST) guideline (version 1.1).⁴¹ Changes in the largest diameter (unidimensional measurement) of the tumor lesions and the shortest diameter in the case of malignant lymph nodes are used in the RECIST criteria.

12.2 Disease Parameters

Measurable disease: Measurable lesions are defined as those that can be accurately measured in at least one dimension (longest diameter to be recorded) as >20 mm by chest x-ray, as >10 mm with CT scan, or >10 mm with calipers by clinical exam. All tumor measurements must be recorded in millimeters (or decimal fractions of centimeters).

Malignant lymph nodes: To be considered pathologically enlarged and measurable, a lymph node must be >15 mm in short axis when assessed by CT scan (CT scan slice thickness recommended to be no greater than 5 mm). At baseline and in follow-up, only the short axis will be measured and followed.

Non-measurable disease: All other lesions (or sites of disease), including small lesions (longest diameter <10 mm or pathological lymph nodes with ≥10 to <15 mm short axis), are considered non-measurable disease. Bone lesions, leptomeningeal disease, ascites, pleural/pericardial effusions, lymphangitis cutis/pulmonitis, inflammatory breast disease, and abdominal masses (not followed by CT or MRI), are considered as non-measurable.

Note: Cystic lesions that meet the criteria for radiographically defined simple cysts should not be considered as malignant lesions (neither measurable nor non-measurable) since they are, by definition, simple cysts.

'Cystic lesions' thought to represent cystic metastases can be considered as measurable lesions, if they meet the definition of measurability described above. However, if non-cystic lesions are present in the same patient, these are preferred for selection as target lesions.

Target lesions: All measurable lesions up to a maximum of 2 lesions per organ and 5 lesions in total, representative of all involved organs, should be identified as target lesions and recorded and measured at baseline. Target lesions should be selected on the basis of their size (lesions with the longest diameter), be representative of all involved organs, but in addition should be those that lend themselves to reproducible repeated measurements. It may be the case that, on occasion, the largest lesion does not lend itself to reproducible measurement in which circumstance the next largest lesion which can be measured reproducibly should be selected. A sum of the diameters (longest for non-nodal lesions, short axis for nodal lesions) for all target lesions will be calculated and reported as the baseline sum diameters. If lymph nodes are to be included in the sum, then only the short axis is added into the sum. The baseline sum diameters will be used as reference to further characterize any objective tumor regression in the measurable dimension of the disease.

Non-target lesions: All other lesions (or sites of disease) including any measurable lesions over and above the 5 target lesions should be identified as non-target lesions and should also be recorded at baseline. Measurements of these lesions are not required, but the presence, absence, or in rare cases unequivocal progression of each should be noted throughout follow-up.

12.3 Methods for Evaluation of Measurable Disease

All measurements should be taken and recorded in metric notation using a ruler or calipers. All baseline evaluations should be performed as closely as possible to the beginning of treatment and never more than 4 weeks before the beginning of the treatment.

The same method of assessment and the same technique should be used to characterize each identified and reported lesion at baseline and during follow-up. Imaging-based evaluation is preferred to evaluation by clinical examination unless the lesion(s) being followed cannot be imaged but are assessable by clinical exam.

Clinical lesions: Clinical lesions will only be considered measurable when they are superficial (e.g., skin nodules and palpable lymph nodes) and ≥10 mm diameter as assessed using calipers (e.g., skin nodules). In the case of skin lesions, documentation by color photography, including a ruler to estimate the size of the lesion, is recommended.

Chest x-ray: Lesions on chest x-ray are acceptable as measurable lesions when they are clearly defined and surrounded by aerated lung. However, CT is preferable.

Conventional CT and MRI: This guideline has defined measurability of lesions on CT scan based on the assumption that CT slice thickness is 5 mm or less. If CT scans have slice thickness greater than 5 mm, the minimum size for a measurable lesion should be twice the slice thickness. MRI is also acceptable in certain situations (e.g. for body scans).

Use of MRI remains a complex issue. MRI has excellent contrast, spatial, and temporal resolution; however, there are many image acquisition variables involved in MRI, which greatly impact image quality, lesion conspicuity, and measurement. Furthermore, the availability of MRI is variable globally. As with CT, if an MRI is performed, the technical specifications of the scanning sequences used should be optimized for the evaluation of the type and site of disease. Furthermore, as with CT, the modality used at follow-up should be the same as was used at baseline and the lesions should be measured/assessed on the same pulse sequence. It is beyond the scope of the RECIST guidelines to prescribe specific MRI pulse sequence parameters for all scanners, body parts, and diseases. Ideally, the same type of scanner should be used and the image acquisition protocol should be followed as closely as possible to prior scans. Body scans should be performed with breath-hold scanning techniques, if possible.

PET-CT: At present, the low dose or attenuation correction CT portion of a combined PET-CT is not always of optimal diagnostic CT quality for use with RECIST measurements. However, if the site can document that the CT performed as part of a PET-CT is of identical diagnostic quality to a diagnostic CT (with IV and oral contrast), then the CT portion of the PET-CT can be used for RECIST measurements and can be used interchangeably with conventional CT in accurately measuring cancer lesions over time. Note, however, that the PET portion of the CT introduces additional data which may bias an investigator if it is not routinely or serially performed.

Ultrasound: Ultrasound is not useful in assessment of lesion size and should not be used as a method of measurement. Ultrasound examinations cannot be reproduced in their entirety for independent review at a later date and, because they are operator dependent, it cannot be guaranteed that the same technique and measurements will be taken from one assessment to the next. If new lesions are identified by ultrasound in the course of the study, confirmation by CT or MRI is advised. If there is concern about radiation exposure at CT, MRI may be used instead of CT in selected instances.

Endoscopy, Laparoscopy: The utilization of these techniques for objective tumor evaluation is not advised. However, such techniques may be useful to confirm complete pathological response when biopsies are obtained or to determine relapse in trials where recurrence following complete response (CR) or surgical resection is an endpoint.

Tumor markers: Tumor markers alone cannot be used to assess response. If markers are initially above the upper normal limit, they must normalize for a patient to be considered in complete clinical response. Specific guidelines for both CA-125 response (in recurrent ovarian cancer) and PSA response (in recurrent prostate cancer) have been published [JNCI 96:487-488, 2004; J Clin Oncol 17, 3461-3467, 1999; J Clin Oncol 26:1148-1159, 2008]. In addition, the Gynecologic Cancer Intergroup has developed CA-125 progression criteria which are to be integrated with objective tumor assessment for use in first-line trials in ovarian cancer [JNCI 92:1534-1535, 2000].

Cytology, Histology: These techniques can be used to differentiate between partial responses (PR) and complete responses (CR) in rare cases (e.g., residual lesions in tumor types, such as germ cell tumors, where known residual benign tumors can remain).

The cytological confirmation of the neoplastic origin of any effusion that appears or worsens during treatment when the measurable tumor has met criteria for response or stable disease is mandatory to differentiate between response or stable disease (an effusion may be a side effect of the treatment) and progressive disease.

FDG-PET: While FDG-PET response assessments need additional study, it is sometimes reasonable to incorporate the use of FDG-PET scanning to complement CT scanning in assessment of progression (particularly possible 'new' disease). New lesions on the basis of FDG-PET imaging can be identified according to the following algorithm:

- Negative FDG-PET at baseline, with a positive FDG-PET at follow-up is a sign of PD based on a new lesion.
- No FDG-PET at baseline and a positive FDG-PET at follow-up: If the positive FDG-PET at follow-up corresponds to a new site of disease confirmed by CT, this is PD. If the positive FDG-PET at follow-up is not confirmed as a new site of disease on CT, additional follow-up CT scans are needed to determine if there is truly progression occurring at that site (if so, the date of PD will be the date of the initial abnormal FDG-PET scan). If the positive FDG-PET at follow-up

- corresponds to a pre-existing site of disease on CT that is not progressing on the basis of the anatomic images, this is not PD.
- FDG-PET may be used to upgrade a response to a CR in a manner similar to a biopsy in cases where a residual radiographic abnormality is thought to represent fibrosis or scarring. The use of FDG-PET in this circumstance should be prospectively described in the protocol and supported by disease-specific medical literature for the indication. However, it must be acknowledged that both approaches may lead to false positive CR due to limitations of FDG-PET and biopsy resolution/sensitivity.

Note: A 'positive' FDG-PET scan lesion means one which is FDG avid with an uptake greater than twice that of the surrounding tissue on the attenuation corrected image.

12.4 Response Criteria

12.4.1 Evaluation of Target Lesions

Complete Response (CR): Disappearance of all target lesions. Any pathological lymph nodes (whether target or non-target) must have reduction in short axis to <10 mm.

Partial Response (PR): At least a 30% decrease in the sum of the diameters of target lesions, taking as reference the baseline sum diameters.

Progressive Disease (PD): At least a 20% increase in the sum of the diameters of target lesions, taking as reference the smallest sum on study (this includes the baseline sum if that is the smallest on study). In addition to the relative increase of 20%, the sum must also demonstrate an absolute increase of at least 5 mm. (Note: the appearance of one or more new lesions is also considered progressions).

Stable Disease (SD): Neither sufficient shrinkage to qualify for PR nor sufficient increase to qualify for PD, taking as reference the smallest sum diameters while on study.

12.4.2 Evaluation of Non-Target Lesions

Complete Response (CR): Disappearance of all non-target lesions and normalization of tumor marker level. All lymph nodes must be non-pathological in size (<10 mm short axis).

Note: If tumor markers are initially above the upper normal limit, they must normalize for a patient to be considered in complete clinical response.

Non-CR/Non-PD: Persistence of one or more non-target lesion(s) and/or maintenance of tumor marker level above the normal limits.

Progressive Disease (PD): Appearance of one or more new lesions and/or unequivocal progression of existing non-target lesions. Unequivocal progression should not normally trump target lesion status. It must be representative of overall disease status change, not a single lesion increase.

Although a clear progression of "non-target" lesions only is exceptional, the opinion of the treating physician should prevail in such circumstances, and the progression status should be confirmed at a later time by the review panel (or Principal Investigator).

12.4.3 Evaluation of Best Overall Response

The best overall response is the best response recorded from the start of the treatment until disease progression/recurrence (taking as reference for progressive disease the smallest measurements recorded since the treatment started). The patient's best response assignment will depend on the achievement of both measurement and confirmation criteria.

For Patients with Measurable Disease (i.e., Target Disease)

For Tatients with Measurable Disease (i.e., Target Disease)				
Target	Non-Target	New	Overall	Best Overall Response
Lesions	Lesions	Lesions	Response	when Confirmation is
			_	Required*
CR	CR	No	CR	>4 wks. Confirmation**
CR	Non-CR/Non-	No	PR	
	PD			
CR	Not evaluated	No	PR	>4 wks. Confirmation**
PR	Non-CR/Non-	No	PR	24 wks. Commination .
	PD/not			
	evaluated			
SD	Non-CR/Non-	No	SD	Documented at least once
	PD/not			>4 wks. from baseline**
	evaluated			24 WKS. Holli baselille
PD	Any	Yes or	PD	
		No		
Any	PD***	Yes or	PD	no prior SD, PR or CR
		No		
Any	Any	Yes	PD	

^{*} See RECIST 1.1 manuscript for further details on what is evidence of a new lesion.

Note: Patients with a global deterioration of health status requiring discontinuation of treatment without objective evidence of disease progression at that time should be reported as "symptomatic deterioration." Every effort should be made to document the objective progression even after discontinuation of treatment.

^{**} Only for non-randomized trials with response as primary endpoint.

^{***} In exceptional circumstances, unequivocal progression in non-target lesions may be accepted as disease progression.

For Patients with Non-Measurable Disease (i.e., Non-Target Disease)

Non-Target Lesions	New Lesions	Overall Response
CR	No	CR
Non-CR/non-PD	No	Non-CR/non-PD*
Not all evaluated	No	not evaluated
Unequivocal PD	Yes or No	PD
Any	Yes	PD

^{* &#}x27;Non-CR/non-PD' is preferred over 'stable disease' for non-target disease since SD is increasingly used as an endpoint for assessment of efficacy in some trials so to assign this category when no lesions can be measured is not advised

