5.3 Evaluability

All patients who receive any study treatment are evaluable for toxicity. Patients are evaluated from first receiving study treatment until a 30-day follow up after the conclusion of treatment or death.

All patients are evaluable for disease response unless they discontinue treatment prior to completion of Cycle 4 and have not had any disease assessment.

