5.6 Duration of Therapy

If at any time the constraints of this protocol are considered to be detrimental to the patient's health and/or the patient no longer wishes to continue protocol therapy, the protocol therapy should be discontinued and the reason(s) for discontinuation documented

Protocol Version: 10Jun2022 – Amendment 6 Page 20 of 64

in the case report forms.

In the absence of treatment delays due to adverse events, treatment may continue indefinitely or until one of the following criteria applies:

- Documented and confirmed disease progression
- Death
- Adverse event(s) that, in the judgment of the investigator, may cause severe or permanent harm or which rule out continuation of study drug, including:
 - o Grade 3 or 4 infusion reaction
 - o Grade 4 hypertension
 - o Grade 3 or 4 arterial thromboembolic event, or any PE/DVT occurring or worsening during anticoagulant therapy
 - One occurrence of urine protein level > 3 g/24 hours, three occurrences of urine protein level > 2 g/24, or urine protein level > 2 g/24 hours for more than 2 weeks
 - o Gastrointestinal perforation or fistula formation
 - o RPLS
 - Hepatic encephalopathy or other serious signs of liver impairment such as hepatorenal syndrome
- General or specific changes in the patient's condition render the patient unable to receive further treatment in the judgment of the investigator
- Suspected pregnancy
- Serious non-compliance with the study protocol
- Lost to follow-up
- Patient withdraws consent
- Investigator removes the patient from study
- The Siteman Cancer Center decides to close the study

Patients who prematurely discontinue treatment for any reason will be followed as indicated in the study calendar.

5.7 **Duration of Follow-up**

Patients will be followed every 2 months after discontinuation of treatment for progression and survival for 30 months. Patients removed from study for unacceptable adverse events will be followed until resolution or stabilization of the adverse event.

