15.3 Secondary Efficacy Measures

- Overall Survival Time (OS):
 - OS time will be measured from date of study entry to date of death from any cause. For those who are alive, we censor them at the time of loss to follow-up (very few) or at 30 months from the date of treatment discontinuation, which come first.
- Time to Progressive Disease (TTP):
 - TTP is defined as the time from study entry until date of radiographic PD using RECIST v1.1 criteria. For those who are alive and do not experience progression, we censor them at the time of loss to follow-up (very few) or at 12 months from the study entry, which come first. For those who are dead before progression, we will consider death as the competing risk. If the number of death are very small, we will censor them at time of death.
- Best Overall Response (BOR) of Complete Response (CR), Partial Response (PR), Stable Disease (SD) or PD:
 - BOR is defined as the best response across all time points from randomization until radiologically confirmed PD using RECIST, v1.1 criteria. CR is defined as the disappearance of all target and non-target lesions and any pathological lymph nodes (whether target or non-target) must have reduction in short axis to <10 mm and normalization of tumor marker level of non-target lesions. PR is defined as having a \geq 30% decrease in sum of longest diameter (LD) of target lesions. PD was defined as having a \geq 20% increase in sum of LD of target lesions and \geq 5 mm increase above nadir. SD was defined as small changes that did not meet above criteria.
- Objective Response Rate (ORR):
 ORR is defined as the percentage of participants with confirmed CR or confirmed PR.
- Clinical Benefit Rate (CBR):
 CBR is defined as percentage of combined patients who have achieved confirmed CR,
 PR and SD.

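### The best-response window closes only at progression, so shrinkage on a later anticancer therapy can be credited to irinotecan plus ramucirumab in BOR and ORR

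*Combined protocol and SAP*

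**What the plan says.** The plan defines the best-response window twice.

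- Section 12.4.3: "The best overall response is the best response recorded from the start of the treatment until disease progression/recurrence".
- Section 15.3: "BOR is defined as the best response across all time points from randomization until radiologically confirmed PD using RECIST, v1.1 criteria". The trial has a single arm (section 15.1), so there is no randomization to start from.

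Two response rates are built on this:

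- "ORR is defined as the percentage of participants with confirmed CR or confirmed PR" (section 15.3).
- "CBR is defined as percentage of combined patients who have achieved confirmed CR", PR or SD (section 15.3).

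Scan collection continues after study treatment ends. Section 12.1 says "Information from lesion evaluation by imaging done as part of routine care will be collected until progressive disease has been objectively determined", and both it and footnote 3 of the section 10.0 calendar apply this "if the patient discontinued treatment due to any other reason than progressive disease". Section 5.7 adds: "Patients will be followed every 2 months after discontinuation of treatment for progression and survival for 30 months".

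The response-evaluable set is in section 5.3: "All patients are evaluable for disease response unless they discontinue treatment prior to completion of Cycle 4 and have not had any disease assessment". No section makes a later anticancer therapy a cut-off for BOR, ORR or CBR.

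**The concern.** Secondary objectives 3 to 5 ask for BOR, ORR and CBR in patients treated with irinotecan plus ramucirumab. A best response is a maximum over the scans in the window. If the window stays open after the patient has moved to another regimen, the maximum can be reached on that regimen.

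The plan's own rules make this possible. Section 5.6 lists many reasons for stopping other than progression, including adverse events, withdrawal of consent and investigator decision. Section 12.4.3 adds symptomatic deterioration without objective progression. These patients keep an open response window, their routine scans are collected, and some may receive other therapy. There is no control arm in which the same inflation would occur and cancel.

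**Working it through.** **The plan's own figure.** The only design figure is 85% power for PFS with 40 patients (section 15.1). Inputs: medians 2.5 and 4 months, exponential survival, one-sided alpha 0.05, 12 months of accrual plus 12 months of follow-up.

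- Hazard ratio = 2.5/4 = 0.625.
- Event probability under the alternative p = 0.947. Expected cumulative null hazard v = 0.947/0.625 = 1.516. Variance of the per-patient difference s² = 2.162.
- Power of the one-sample log-rank test = Φ[(√40 × (1.516 − 0.947) − 1.645 × √1.516)/√2.162] = Φ(1.07) = 85.7%, with 39 patients required for 85%.
- With every patient cut off at 12 months, power is 84.8%, with 41 required.

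The figure reproduces. It does not involve the BOR window, and the plan states no target for BOR, ORR or CBR.

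**Following the rules for one patient** (weeks chosen for illustration):

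1. Week 8 scan: SD.
2. Week 10: study treatment stops for toxicity. The last scan is 14 days old, so footnote 4 of the calendar (21 days) waives end-of-treatment imaging.
3. Another anticancer therapy starts.
4. Week 18 routine scan: target sum at least 30% below the pre-treatment baseline, hence PR (section 12.4.1).
5. Week 22 or later: PR again, meeting the 4-week minimum in section 12.1.

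There has been no progression, so both windows are still open. BOR moves from SD to confirmed PR and ORR gains a responder. The confirmation rule gives no protection, because both scans fall on the later therapy.

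**Size for ORR.** Change = k/40, where k is the number of such patients. The documents give no value for k, nor an expected ORR. Taking 8 true responders purely as an illustration:

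| k | Responders | ORR | Exact 95% CI | Change (points) |
|---|---|---|---|---|
| 0 | 8/40 | 20.0% | 9.1–35.6% | 0 |
| 1 | 9/40 | 22.5% | 10.8–38.5% | +2.5 |
| 2 | 10/40 | 25.0% | 12.7–41.2% | +5.0 |
| 3 | 11/40 | 27.5% | 14.6–43.9% | +7.5 |

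If the denominator is the response-evaluable set and is smaller than 40, each case counts for slightly more (1/39 = 2.6 points).

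**Size for CBR.** SD already counts, so an SD-to-PR upgrade changes CBR by 0. CBR can move only for a patient with no on-treatment assessment. Take someone who stops at week 5. Any baseline scan is then at least 35 days old, more than 21, so the calendar requires an end-of-treatment scan. The case arises only if that scan is missed. Under section 5.3 the patient is then not evaluable unless a later scan is admitted. With an illustrative 28/39 for CBR (71.8%) and 8/39 for ORR (20.5%), admitting one later scan gives:

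- later scan SD: CBR 29/40 = 72.5% (+0.7 points), ORR 8/40 = 20.0% (−0.5);
- later scan PD: CBR 28/40 = 70.0% (−1.8), ORR 8/40 = 20.0% (−0.5).

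For this group the effect can go either way.

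**The case against.** The strongest reply is that a narrower reading is available. In the calendar, the row for imaging and RECIST time-point response is marked at screening, every 8 weeks and end of treatment, and is blank under follow-up. Post-treatment scans might be meant only for dating progression. This shows that the intention may be sound, but it does not settle the rule. Footnote 3, which extends scan collection beyond treatment, is attached to that same row. Section 12.4.3 ends the window only at progression or recurrence, and section 15.3 does not limit its time points to scheduled ones.

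It might also be said that RECIST 1.1 covers the matter. The protocol writes its own window twice, and the footnote to the table in section 12.4.3 refers to the RECIST publication only for what counts as a new lesion.

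The argument about frequency stands. A case requires stopping without PD, starting another therapy before PD, a fall of at least 30% from the pre-treatment baseline, and confirmation. With a design median PFS of 4 months, zero cases is plausible.

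A reader might infer more than the documents support:

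- *That affected cases could not be identified afterwards.* Section 11.0 lists form titles, not fields, and the Follow Up Form may already hold the information. Section 12.4.6 also strongly recommends independent review of files and images together. All that can be said is that neither the calendar nor the form list names subsequent therapy.
- *That only patients who could not tolerate the regimen are affected.* Section 5.6 gives other reasons for stopping.

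**Conclusion.** The point holds for BOR and ORR. Applied literally, both definitions credit the study combination with a response first reached on a later anticancer therapy. For patients already assessed on treatment, the error can only raise BOR and ORR or leave them unchanged. It is worth 2.5 points of ORR per case with a denominator of 40. The range of 0 to 7.5 points rests on an assumed 0 to 3 cases.

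A reader might conclude that CBR is inflated by the same amount, or that the bias is upward in every patient. Neither follows: SD-to-PR upgrades leave CBR unchanged, and patients with no on-treatment assessment can move either rate up or down. Nor is the primary result in question, because the BOR window plays no part in the PFS test. BOR, ORR and CBR are secondary, with no threshold or decision rule attached. The change is still worth making: the rule is stated explicitly, it works against the objectives it serves, and correcting it costs little.

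**What to change.** - In sections 12.4.3 and 15.3, define BOR as the best RECIST 1.1 response from first dose of study treatment to the earlier of first documented PD or start of new anticancer therapy.
- State that ORR and CBR use the same window, so that scans after the start of new therapy do not count towards any of the three.
- In section 15.3, replace *randomization* with start of treatment.
- Ensure that the Follow Up Form captures the start date of the first subsequent anticancer therapy.

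The cost is a change of wording in two sections and, if the form lacks it, one date field. No treatment, visit or scan changes. The downside is that reported ORR may be slightly lower.
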